Protocol: Screening assessments (including medical history and physical assessment) will confirm inclusion and exclusion criteria. If participants, who are otherwise eligible, require more time to meet certain eligibility criteria (e.g., additional time to meet one month on a stable dose of antipsychotic), they may proceed to the Abstinence Period and Baseline Neuropsychiatric Assessment Visit, however, participants must meet all applicable eligibility criteria before proceeding to the T1 scan day. Patient eligibility will be reviewed by a study physician prior to the T1 Scan Day.

Abstinence Period: All study participants will be asked to refrain from any cannabis, alcohol, other substance use (except nicotine and caffeine) for a period of 14 days after the screening assessments until the day of T1, described below. (Note: If the study proves not to be feasible with a period of 14 days of abstinence, the PI will decrease the interval to 7 days as in the previous study.) Participants who are in the groups that use marijuana will be told that it can take days or weeks for THC to no longer be detected in the body, instructed about the schedule of assessments to assess/reinforce their abstinence, and educated about cannabis withdrawal. Participants will be assessed for cannabis withdrawal at each visit.) A Timeline Followback (TLFB) interview and urine/breath tests (to confirm substance abstinence) will be obtained approximately 6 times (up to 3x per week with a minimum of once per week) during this period and approximately 3 times per week with a minimum of once per week during the period between T1 and T2 for participants with a CUD. (See details below for Groups 4 and 8 who do not have any history of a substance use disorder) Those whose tests indicate abstinence will receive a \$30 credit to encourage continued abstinence. Study participants and control participants will only progress to the Scan Days of the study if they achieve 14 days of substance abstinence and will only progress to the Baseline Neuropsychiatric Assessments if they achieve 7 days of substance abstinence.

The criteria for determining abstinence will be as follows:

- For alcohol and substances other than cannabis and synthetic cannabinoids, if the person reports being abstinent on the TLFB since last assessment and tests negative for the substance, they will be considered abstinent.
- For cannabis, the following two criteria must be met for the person to be considered abstinent:

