The criteria for determining abstinence for Study Group 8 (Healthy Controls) will be based on the participant's report of abstinence from alcohol and drugs and confirmation by a negative test on the breathalyzer and urine dipstick test for cannabis and other drugs. Participants in Group 8 will not be required to have additional visits 3x per week to encourage abstinence. The criteria for determining abstinence for Study Group 4 (Schizophrenia Only) will be the same with the exception that staff will attempt to contact participants once during each week to assess and encourage further abstinence.

Any substance use other than cannabis by a participant who is abstinent from cannabis shall be reviewed with [name]. Use that is likely to affect the risks to participants or the results of assessments will result in postponement of T1 and T2 Days. An isolated instance of using a substance a few days prior to testing is unlikely to affect the study results or risk; whereas continued regular use of a substance could produce such an effect.

Baseline Neuropsychiatric Testing: After a minimum of 7 days of abstinence, patients will come into the laboratory or their local clinic as applicable for the Baseline Neuropsychiatric Assessments. This testing will include extrapyramidal side effect (EPS) assessment and cognitive testing. If necessary, it may be possible to conduct some or all of this testing during the Scan Days.

Based on participants' prior exposure to MRI scanning, research staff will introduce participants to the scanner procedures, show them the scanner, and teach them relaxation techniques (if they are concerned about being anxious in the scanner.) If the scanner is not available for this purpose during the Baseline Visit, this will be done at the first MRI Visit.

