7. Currently stable in treatment (either on an antipsychotic or not) for the past month as determined by a study physician's review
8. Not seeking treatment for their CUD.

Group 4 - Control participants with SCZ

1. Ages 18 – 55 years old, inclusive
2. Diagnosis of schizophrenia or schizoaffective disorder as confirmed with the SCID
3. Willing to remain abstinent for the 7 days before the baseline assessments and for 14 days before the two scan days. Note: If the 14 day period of abstinence is reduced for the groups with a CUD, it will be reduced for Group 4 also.
4. Psychiatrically stable as indicated by being treated as an outpatient for the past month, as determined by a study physician's review

5. Currently stable in treatment (either on an antipsychotic or not) for the past month as determined by a study physician's review

Groups 5-7 - Control participants with CUD

1. Ages 18 – 55 years old, inclusive
2. Diagnosis of cannabis abuse or dependence as confirmed by the SCID
3. Use of cannabis within the month prior to screening based on the TLFB
4. Willing to remain abstinent for 7 days before the baseline assessments and 14 days before the two scan days. Note: If the 14 day period of abstinence is too great a barrier for participants, the PI may decrease the amount to 7 days.
5. Not seeking treatment for their CUD.

Group 8 – Healthy control participants

1. Ages 18 – 55 years old, inclusive
2. Willing to remain abstinent for the 7 days before the baseline assessments and 14 days before the two scan days. Note: If the 14 day period of abstinence is reduced for the groups with a CUD, it will be reduced for Group 8 also.

Exclusion criteria:

Groups 1-3 with SCZ-CUD

1. Positive symptoms of psychosis (> 4 [moderate]) on any item of the PANSS psychosis subscale (once abstinent) except for the hallucination item. We will exclude for a rating > 5. for this item.
2. Current cocaine/stimulant dependence. (Note: Current alcohol, synthetic cannabis, nicotine, and caffeine abuse or dependence are allowed; current cocaine/stimulant or other drug abuse is allowed provided the person can achieve the required abstinence; past dependence on cocaine/stimulants or other drugs is also allowed)
3. Pharmacological treatment for addiction (e.g., disulfiram, naltrexone, acamprosate, topiramate, varenicline, bupropion) as determined by a study physician's review.
4. Mental retardation

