5. History of head injury with period of unconsciousness or focal brain injury as determined by a study physician's review.
6. Metal objects within the body that would contraindicate an MRI
7. Pregnancy or currently nursing
8. Is deemed inappropriate for the study by the PI (e.g., due to other medical conditions, medication, psychiatric concerns, or other circumstances that could cause safety concerns or impair the person's ability to participate in the study.)
9. Taking clozapine
10. Any condition that would contraindicate use of cannabis or dronabinol.
11. Patients seeking treatment to limit their cannabis use.
12. History of a seizure disorder as determined by a study physician's review

13. Is assessed as being suicidal or violent as determined by a study physician's review.

Group 4 - Control participants with SCZ

1. Positive symptoms of psychosis (> 4 [moderate]) on any item of the PANSS psychosis subscale (once abstinent) except for the hallucination item. We will exclude for a rating > 5. for this item.
2. Any history of a substance use disorder other than nicotine and caffeine.
3. Pharmacological treatment for addiction (e.g., disulfiram, naltrexone, acamprosate, topiramate, varenicline, bupropion) as determined by a study physician's review.
4. Mental retardation
5. History of head injury with period of unconsciousness or focal brain injury as determined by a study physician's review
6. Metal objects within the body that would contraindicate an MRI
7. Pregnancy or currently nursing

8. Is deemed inappropriate for the study by the PI (e.g., due to other medical conditions, medication, psychiatric concerns, or other circumstances that could cause safety concerns or impair the person's ability to participate in the study.)

9. History of a seizure disorder as determined by a study physician's review
10. Taking clozapine
11. Is assessed as being suicidal or violent as determined by a study physician's review.

Groups 5-7 - Control participants with CUD

1. Any Axis I psychiatric diagnosis other than a CUD. (NOTE: Current alcohol, synthetic cannabinoid, nicotine, and caffeine abuse or dependence are allowed. Other substance abuse is allowed provided the person can achieve the required abstinence; past dependence on cocaine/stimulants or other drugs is also allowed. Also, past (but not current) diagnoses of ADHD, depressive disorders and anxiety disorders are allowed.)
2. Taking any psychotropic medication

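### People with current alcohol dependence may enrol and must stop drinking to be scanned, but withdrawal safety measures name only cannabis and no step requires alcohol withdrawal risk to be judged first

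*Combined protocol and SAP*

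**What the plan says.** **Who may enrol.** The note to exclusion 2 for Groups 1-3 (section 5) reads "Current alcohol, synthetic cannabis, nicotine, and caffeine abuse or dependence are allowed". The note to exclusion 1 for Groups 5-7 reads "Current alcohol, synthetic cannabinoid, nicotine, and caffeine abuse or dependence are allowed". Groups 4 and 8 exclude alcohol use disorders, so the point does not reach them.

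**What they are asked to do.** Section 4, Abstinence Period, says "All study participants will be asked to refrain from any cannabis, alcohol, other substance use (except nicotine and caffeine", and sets 14 days of this between screening and T1. The PI may shorten this to 7 days if 14 proves infeasible. Reaching 14 days is a condition for the scan days. Section 29 pays Groups 1-3 and 5-7 for confirmed abstinence.

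**What is checked before and during abstinence.** On screening, section 4 says "Screening assessments (including medical history and physical assessment) will confirm inclusion and exclusion criteria". On timing, it says "Patient eligibility will be reviewed by a study physician prior to the T1 Scan Day". Follow-back interviews and urine or breath tests are "obtained approximately 6 times (up to 3x per week with a minimum of once per week) during this period". On withdrawal, it says "Participants will be assessed for cannabis withdrawal at each visit". Section 10 lists a cannabis withdrawal scale and no alcohol counterpart. The withdrawal paragraph in section 14, with its fact sheet and support route, is about cannabis.

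**The concern.** The plan knowingly admits people with alcohol dependence, asks them to stop, and makes stopping a condition for going on. Its specific withdrawal precautions are built around a different substance, whose withdrawal section 14 describes as not medically dangerous. A dependent drinker who complies could go through the first days without alcohol with nobody having been told to consider that risk, and with visit questions aimed at cannabis.

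The stake is participant safety, not bias or power. The documents do not discuss how serious alcohol withdrawal can be. That it can be dangerous in some dependent drinkers is general clinical knowledge, and the study physicians are the right people to judge it. Section 15 nevertheless tells the ethics committee that no study risk is severe, without having considered this one.

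**Working it through.** No power or sample-size figure is at issue. The check sets the relevant provisions side by side, then sizes what can be sized.

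**1. Does any step before abstinence pick out alcohol withdrawal risk?**
- The SCID and follow-back interview (section 10) would show who is currently dependent. In the six groups there is also a history, physical, EKG and bloods.
- The stated uses are to confirm eligibility (section 4) and to rule out contraindications to dronabinol or cannabis (section 10, Safety Assessment). Current alcohol dependence is allowed, so confirming eligibility does not flag it.
- Abstinence follows screening, so the PI safety exclusion and the seizure-disorder exclusion would normally be applied first. Otherwise eligible people who need more time on certain criteria may start abstinence earlier. The PI exclusion does not mention alcohol. Section 14 links the seizure exclusion to dronabinol.
- The physician eligibility review must precede T1. An earlier review is possible but not required.

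**2. Does any step during abstinence do so?**
- Withdrawal assessment, scale, education and support route: cannabis only.
- Caffeine withdrawal (section 4, Scan Days) and nicotine withdrawal (section 10) are mentioned, but to protect the imaging measures, not for safety.
- Alcohol is followed by self-report and breathalyzer to confirm abstinence.
- Section 4 adds: "Any substance use other than cannabis by a participant who is abstinent from cannabis shall be reviewed with" a designated person. That review is triggered by use. It reaches those who keep drinking, not those who stop.

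**3. Contact frequency in the 14 days**
- Planned: 14 / 6 = 2.3 days between visits.
- Permitted minimum, once a week: 14 / 2 = 7 days between visits.
- The text does not say whether the Baseline visit, due after at least 7 days of abstinence, counts among these.

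**4. Payments (section 29)**
- The plan's own total reproduces: 9 x ($10 + $30) = $360, plus 3 x $30 = $90, gives $450.
- Part that depends on confirmed abstinence: 9 x $30 + 3 x $30 = $360, or 360 / 450 = 80%.
- Part available before the T1 day, with Baseline as a separate visit: 6 x $30 + $30 = $210 as planned; 2 x $30 + $30 = $90 at the minimum.
- Scan-day stipends, normally reached only by abstaining: $100 + $200 = $300 in Groups 1-3; $400 + $500 = $900 in Groups 5-7.

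**5. How many people?**
- Groups open to current alcohol dependence: 6 x 25 = 150 of 200.
- The documents give no prevalence. As an assumption for scale only, 2%, 10% or 20% gives 0.02 x 150 = 3, 0.10 x 150 = 15, or 0.20 x 150 = 30 people.
- Section 4 expects 400 recruited to obtain 200, so more than 150 could begin abstinence. The split by group is not given.

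**The case against.** The best reply is that the plan already has working safeguards and lacks only a label. Much of this stands:
- Screening normally applies the PI safety exclusion before abstinence begins, and that exclusion is broad enough to cover withdrawal risk.
- Section 15 says people thought unable to tolerate the procedures will not be included, and abstinence is one of those procedures.
- Adverse events are reviewed at each visit (section 10).
- Psychiatrists are on call (section 14). Section 18 adds 24-hour clinicians, and phones for those who need one.
- Participants with schizophrenia have a prescriber and treatment team (the resources items before section 18).

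A reader might therefore infer too much from the gap: that nobody considers safety before drinking stops, or that adverse event review is the only means of detection. The documents do not support either. Nor do they support reading the payments as pressure to stop alcohol in particular. The money covers all substances together, and section 4 treats an isolated non-cannabis lapse as unlikely to matter.

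What the reply does not answer is that every safeguard is general. None tells anyone to use the alcohol data for this purpose before cessation. The treatment-team backstop is also weaker for Groups 5-7, who are recruited by advertising and are not receiving treatment (section 25 and Attachment B).

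**Conclusion.** The point holds as a gap in specific protection, not as an absence of protection. The plan admits people with current alcohol dependence, requires them to abstain in order to be scanned, and pays for abstinence. In the available text its withdrawal safety measures name only cannabis, and no step requires alcohol withdrawal risk to be judged before drinking stops. At the permitted minimum, run-in contact could be weekly.

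This goes beyond missing detail, because the eligibility check cannot flag a condition that the criteria allow. It should be fixed.

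The number affected is unknown. A reader might take 150 as the number at risk, but it is only the planned size of the groups in which dependence is allowed, and 3 to 30 rests on assumed prevalences. Nor do the documents show how many participants with this diagnosis would be physically dependent when they stop.

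Confidence is moderate. The consent pages, a stretch of text before section 18 and the attached schedule of events were not available, and any of them could name the risk or list a relevant check.

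**What to change.** 1. For participants with current alcohol dependence on the SCID, require the study physician to review alcohol withdrawal risk from the existing screening data before the abstinence period starts. Exclude or refer under the existing PI safety criterion where needed.
2. For these participants, add brief alcohol-withdrawal items at the run-in visits already planned. The physician can decide whether an early visit or call is needed.
3. Extend the education and clinical-support route in section 14 from cannabis to alcohol.
4. Name alcohol withdrawal in section 14, and revise the statement in section 15 that no risk is severe.

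The study physicians should set the clinical content. The cost is a protocol amendment, an earlier review for a subset, a few added items or calls, and a slightly smaller recruitment pool. Alcohol dependence need not become an exclusion, and the endpoints and analyses do not change.
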